#### **4.4.6.3 Withdrawal from Study**

Patients are at any time free to withdraw from study (investigational product and assessments), without prejudice to further treatment (withdrawal of consent). Such patients will always be asked about the reason(s) and the presence of any adverse events. If possible, they will be seen and assessed by an Investigator. Adverse events will be followed up (See Sections 5.10.3 and 5.10.4), diary cards and study drug should be returned by the patient.

Withdrawn patients will not be replaced

Reasons for withdrawal from the study:

- Voluntary withdrawal by the patient who is at any time free to discontinue their participation in the study, without prejudice to further treatment
- Risk to patients as judged by the Investigator and /or AstraZeneca
- Severe non-compliance to protocol as judged by the Investigator and/or AstraZeneca
- Incorrectly enrolled patients i.e., the patient does not meet the required inclusion/exclusion criteria for the study
- The patient becomes pregnant
- Patient lost to follow-up

#### **4.4.6.4 (PGx:) Procedures for Discontinuation from Genetic aspects of the Study**

Patients who discontinue from the study should always be asked specifically whether they are withdrawing or continuing their consent for this linked genetic research. It must be established whether the patient:

- Agrees to the genetic sample and any DNA extracted from the sample being kept for genetic analyses in the future.
- Withdraws consent for the sample to be kept for genetic analysis in the future and wishes the sample to be destroyed. Destruction of the sample (or the DNA extracted from the sample) will only be possible so long as the particular sample is

traceable. In the event that genetic research has already been performed, AstraZeneca will retain the results and associated data for regulatory reasons but these will not be used in any subsequent analyses.

The principal investigator is responsible for providing written notification to AstraZeneca of any patient who has withdrawn consent for the use of the sample taken for genetic research. AstraZeneca will provide written confirmation to the investigator of the actions taken with the sample, which must be filed in the investigator study file.

## 4.5 Treatment(s)

### 4.5.1 Investigational product(s)

#### 4.5.1.1 Identity of investigational product

AZD2281 is a white to off-white crystalline solid with a molecular weight of 434 Da. The molecular formula is  $C_{24}H_{23}FN_4O_3$ .

Micronised AZD2281 will be supplied as an oral capsule, with Gelucire 44/14 (Lauroylmacroglycerides) as excipients (solubiliser).

Capsules will be Vcaps® Hydroxypropyl Methylcellulose Capsugel® Capsules which are not banded or enteric coated.

For this study, capsules are in one dosage strength: 50 mg, Size 0, coloured white.

Investigational product	Dosage form and strength	Manufacturer	Formulation Number	Batch number
AZD2281	50 mg	Patheon Inc on behalf of AstraZeneca	F13579	TBC a

a Batch numbers not currently available, these will be detailed in the Clinical Study Report

#### 4.5.1.2 Labelling

AZD2281 will be supplied in High Density Polyethylene containers with a child-resistant cap. Patients will be given sufficient supplies for a dispensing visit, multiple capsules /bottles may be required to make up the dose.

The Investigator / site staff should dispense one or more bottles to the patient as required, in order to make up the assigned dose of AZD2281. Each container of AZD2281 will have an investigational-use label permanently affixed to the outside and will be labelled in accordance with Good Manufacturing Practice and local regulations, The labels will fulfil GMP Annex 13 requirements for labelling. Label text will be translated into local language stating that the drug is for clinical trial use only and should be kept out of reach of children. The label will include the dosing instructions and a space for the enrolment code (E-code) to be completed at

the time of dispensing. Each label will also include a tear-off portion that should be applied to individual patient CRF/drug accountability forms, upon dispensing.

Centres will use their commercial supply of cisplatin for this trial. In situations where the cost of the drug is not covered by third party payment (ie, insurance) then centres will be reimbursed for the cost of the drug. Cisplatin should be stored, reconstituted and administered according to the manufacturers' recommendation. Details of each dose administered and the duration of infusion must be recorded in the Case Report Forms.

#### **4.5.1.3 Storage**

All investigational products must be kept in a secure place under appropriate storage conditions and may only be dispensed by a pharmacist or a qualified designee. A description of the appropriate storage and shipment conditions are specified on the investigational product label.

#### **4.5.1.4 Accountability**

The medication provided for this study is for use only as directed in the protocol. It is the investigator/institution's responsibility to establish a system for handling trial treatments, including investigational medicinal products, so as to ensure that:

- deliveries of such products from AstraZeneca are correctly received by a responsible person
- such deliveries are recorded
- study treatments are handled and stored safely and properly
- study treatments are only dispensed to study patients in accordance with the protocol

### **4.5.2 Doses and treatment regimens**

#### **4.5.2.1 AZD2281**

The doses of AZD2281 will be made up from 50 mg capsules to be taken twice daily either continuously or intermittently. Patients should swallow the medication whole with a glass of water in the morning and in the evening at the same time each day. This is to ensure approximately a 12-hour interval between doses. The dose of AZD2281 should be taken no sooner than 1 hour after food and patient should refrain from eating for 2 hours after dosing due to potential effect of food on absorption. The olaparib capsules should be swallowed whole and not chewed, crushed, dissolved or divided.

If vomiting occurs shortly after the AZD2281 capsules are swallowed, the dose should only be replaced if all of the intact capsules can be seen and counted. Should any patient enrolled on the study miss a scheduled dose for whatever reason (e.g., as a result of forgetting to take the capsules or vomiting), the patient will be allowed to take the scheduled dose up to a maximum

of 2 hours after that scheduled dose time. If greater than 2 hours after the scheduled dose time, the missed dose is not to be taken and the patient should take their allotted dose at the next scheduled time.

Up to 1 week before the start of combination treatment patients allocated to receive continuous dosing will attend the clinic to receive a single dose of AZD2281, PK samples over 12 hours will be obtained to get monotherapy PK information. PK blood draws will not be performed for patients enrolled into an intermittent dosing cohort.

#### 4.5.2.2 Cisplatin

Cisplatin should be prepared in accordance with the local prescribing guidelines. Cisplatin will be administered 2 hours (+/- 1 hour) after the first (morning) dose of AZD2281 every 3 weeks.

- **Dose:** cisplatin 75 mg/m^2 IV q3 weeks or cisplatin 60 mg/m^2 IV q3 weeks
- **Infusion Time:** 60 minutes.
- **Anti-Emetic Premedication.** Patients should receive prophylactic anti-nausea medications such as ondansetron 24 mg po/iv x 1, dexamethasone 10 mg –20 mg po/iv x 1, prochlorperazine 10 mg po x 1 prn, and/or lorazepam 1 mg iv/po x 1 prn prior to cisplatin therapy.
- **Pretreatment Hydration:** Hydration may be achieved by IV infusion of 1 litre of sodium chloride 0.9% over 1-2 hours prior to cisplatin infusion
- **Treatment:** Give 12.5 gm iv of mannitol 20% or mannitol 25% 30 minutes prior to cisplatin infusion. Mix cisplatin in 100-500 ml sodium chloride 0.9% and infuse IV over 60 minutes. Ensure there is adequate urine output averaging at least 100cc/hr prior to cisplatin infusion
- **Post treatment Hydration:** Patient should receive 1 litre of sodium chloride 0.9% iv over 1-2 hours after cisplatin administration.

In this phase I study, after patients have completed 4 cycles of cisplatin based therapy at the full dose of 75 mg/m^2, or a dose of 60 mg/m^2 for those patients that received the lower cisplatin dosing treatment cohort option, subsequent cycles of cisplatin may be administered at a reduced dose as low as and including 50 mg/m^2 at the investigator's discretion as long as the patient is continuing to derive clinical benefit and has not met the criteria for progressive disease or any other discontinuation criteria. (see section [4.4.6.1](#))

In this study, after patients complete 6 cycles of cisplatin based therapy, cisplatin may be discontinued and AZD2281 may be continued at the optimal monotherapy dose (i.e., 400 mg bid) at the investigators discretion, as long as the patient is continuing to derive clinical benefit and has not met the criteria for progressive disease or any other discontinuation criteria. See [Table 5](#)

## Supplementation:

- **Magnesium supplementation:** Give prior to cisplatin, magnesium sulfate 2 g IV x 1. Patient to take 500 mg magnesium gluconate qd for 7 days. Magnesium level will be checked on day 7 and if <1.8 mg/dL, then magnesium supplementation should continue and adjusted at the physician's discretion.
- **Potassium supplementation:** give Potassium 30-40 mEq/day po for 7 days after each dose. Potassium level will be checked on day 7. If the measurement is <3.5 mmol/L, then potassium supplementation should be continued and adjusted at the physician's discretion.

### 4.5.3 Management of Toxicity

#### 4.5.3.1 Management of Hematological Toxicity (cisplatin and AZD2281)

The following hematologic criteria must be met on Day 1 of each cycle to administer dosing of cisplatin and AZD2281:

- ANC  $\geq 1.5 \times 10^9/L$
- Platelet count  $\geq 100 \times 10^9/L$

If both of these criteria are not met, both cisplatin and AZD2281 should be held for up to a total of 14 days until neutrophils and platelets have recovered to meet the above criteria. If cisplatin and AZD2281 must be held for greater than 14 days and the above hematologic criteria are not met, the patient should be removed from the study. Growth factor is not to be used during cycle 1 (ie any time prior to the second dose of cisplatin). Growth factor can be administered as required after the second dose of cisplatin.

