#### **4.1.2 Dose Limiting Toxicity**

Toxicity will be graded using the NCI Common Terminology Criteria for Adverse Events (NCI CTCAE) Version 3.0. Dose-limiting toxicity (DLT) is defined as the following study drug-related events experienced during Cycle 1:

- Grade 4 thrombocytopenia.
- Grade 4 neutropenia lasting >5 days.
- Febrile neutropenia (ANC <1.0 x10^9/L with fever ≥38.5°C).
- Treatment delay of >2 weeks.

- Other Grade 3 non-haematological toxicities; excluding non-optimally treated nausea, vomiting and diarrhea

Patients with dose-limiting toxicity after cycle 1 who have documented clinical benefit (stable disease or an objective response) may continue to be treated at a reduced dose level if considered clinically appropriate by the investigator.

Any patient in whom a DLT occurs during any cycle will have his or her treatment delayed until toxicity resolves to grade 1 or below.

[figure not shown]

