#### 4.5.3.2 Management of Neutropenic Events

Cisplatin and AZD2281 may not be dosed until ANC  $\geq 1.5 \times 10^9/L$

Filgrastim or PEG-filgrastim may be instituted at the investigator's discretion at any time following completion of cycle 1. Cycle 1 is defined as the time period up until the second dose of cisplatin dose is administered). Filgrastim or PEG-filgrastim may be used at the investigator's discretion during cycle 1 only in the event of febrile neutropenia occurring during cycle 1.

Filgrastim doses can be rounded to within (plus or minus) 10% of the contents of one commercial vial or combinations of the commercial products; i.e., 300 or 480 micrograms/vial.

Each of the following neutropenic events will be managed in a sequential fashion as described in [Table 6](#).

1. ANC  $<1.0 \times 10^9/L$  on Day 1 of a cycle

2. Febrile neutropenia (ANC  $<1.0 \times 10^9/L$  with fever  $\geq 38.5^\circ C$ ) at any time
3. CTCAE grade 4 neutropenia (ANC  $<0.5 \times 10^9/L$ ) lasting longer than 5 days in the middle of a cycle

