#### 4.5.7 Other Concomitant Medications

Any medications, with the exceptions noted in Section 4.5.10 below, which are considered necessary for the patient's welfare, and which it is believed will not interfere with the study medication, may be given at the discretion of the Investigator, providing the medications, the doses, dates and reasons for administration are recorded in the CRF. All relevant concomitant medications, including those stopped within 6 weeks of first dose of AZD2281, should be recorded in the CRF, up until the 30 day follow up date

In addition, any unplanned diagnostic, therapeutic or surgical procedure performed during the study period must be recorded in the CRF.

Between study visits, in order to verify dosing compliance and times of administration of AZD2281, patients will be asked to complete details of any self-medication in a diary card, and during the study visits special attention will be paid to questioning patients in relation to any self-medication.

**Anticoagulant Therapy:** Patients who are taking warfarin may participate in this study; however, it is recommended that prothrombin time (INR and APTT) be monitored carefully at least once per week for the first month, then monthly if the INR is stable. Subcutaneous heparin is permitted.

**Anti-emetics:** Routine prophylactic anti-emetic therapy to be administered according to local practice guidelines.

Prophylaxis with granulocyte colony stimulating factor (G-CSF or Neulasta) / granulocyte-macrophage colony-stimulating factor (GM-CSF) and erythropoietin are prohibited in any arm of the study during the first cycle of therapy. It should only be used during the study after a relevant AE has occurred. In this case, their use is permitted at the Investigator's discretion and according to local hospital guidelines. However, if the patient has an Absolute Neutrophil Count <500 for at least 7 days or fails to recover to the required neutrophil count within 14 days or has febrile neutropaenia, then the use of G-CSF or GM-CSF is permitted in accordance with local clinical practice.

The reason(s) for the use, doses and dates of treatment should be recorded in the patient's medical records and appropriate section of the CRF.

All medications (prescriptions or over-the-counter medications) continued at the start of the study or started during the study or until 30 days from the end of the last protocol treatment and different from the study medication must be documented.

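### The Cycle 1 growth-factor rules contradict each other, and use under the looser ones could remove a duration-based DLT from the count

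*Protocol*

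**What the plan says.** Five places in the protocol govern growth factor in Cycle 1.

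- **Section 4.5.3.1:** "Growth factor is not to be used during cycle 1", which the section defines as the time before the second cisplatin dose. No exception is given.
- **Section 4.5.3.2:** filgrastim or PEG-filgrastim "may be used at the investigator's discretion during cycle 1 only in the event of febrile neutropenia occurring during cycle 1". Cycle 1 is again defined as running to the second cisplatin dose.
- **Section 4.5.7:** prophylactic G-CSF, GM-CSF and erythropoietin "are prohibited in any arm of the study during the first cycle of therapy". The paragraph continues: "It should only be used during the study after a relevant AE has occurred", and then "In this case, their use is permitted at the Investigator's discretion and according to local hospital guidelines". A further sentence permits use for ANC below 500 for at least 7 days, for no recovery of the neutrophil count within 14 days, or for febrile neutropenia.
- **Section 4.5.10:** only prophylactic cytokines are barred in the first cycle.
- **Table 6:** footnote b leaves filgrastim for neutropenic events to the investigator with no cycle limit. Footnote e, on the same column headings, allows growth factor after the second cisplatin dose.

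Section 4.1.2 lists the Cycle 1 DLTs. Two depend on duration: "Grade 4 neutropenia lasting >5 days", and a treatment delay of more than 2 weeks. Sections 4.1.1 and 7.4.5 make a patient evaluable after one cisplatin cycle with at least 75% of planned AZD2281, or on a DLT. Neither mentions growth factor.

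**The concern.** The DLT count in cohorts of 3 to 6 patients decides whether AZD2281 is escalated and where the MTD lies. A DLT defined by how long neutropenia lasts is counted consistently only if treatment that shortens neutropenia is handled in the same way for every patient. Here a site can cite the protocol for a total ban, for a ban with one exception, or for a ban on prophylaxis alone.

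If a site acts on the most permissive text, a patient heading for a duration-based DLT may recover before the threshold. Nothing in the evaluability definition separates that patient from one who never had the toxicity. The error can only take DLTs out of the count, so it runs in one direction, towards a higher MTD.

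**Working it through.** The protocol states no operating characteristic on this point, so there is no figure to reproduce. The check has two parts.

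**1. Which permissions can cost a DLT?**

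| Permission in Cycle 1 | Has a DLT already been met when it applies? | Can it hide a DLT? |
|---|---|---|
| Febrile neutropenia (4.5.3.2, 4.5.7) | Yes. 4.1.2 lists febrile neutropenia, with the same ANC and temperature limits as 4.5.3.2 | No |
| ANC below 500 for at least 7 days (4.5.7) | Yes. 4.5.3.2 gives Grade 4 as ANC below 0.5 x 10^9/L, and 7 days exceeds 5 | No |
| No recovery within 14 days (4.5.7) | It falls at the 2-week delay limit; 4.5.7 does not say from when the 14 days run | Little room |
| After a relevant adverse event (4.5.7) | Not necessarily. No grade, duration or cycle is stated | Yes |
| Table 6 footnote b | Not necessarily. The events that 4.5.3.2 sends to Table 6 include ANC below 1.0 x 10^9/L on Day 1 of a cycle, which is not itself a DLT | Yes |

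The last two rows open two routes. First, growth factor started early in Grade 4 neutropenia could end it within 5 days. Second, a patient with low neutrophils on the planned Day 1 of Cycle 2 is still in Cycle 1 as 4.5.3.1 and 4.5.3.2 define it, because the second cisplatin dose has not been given. Growth factor at that point could end the delay before it exceeds 2 weeks.

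Such a patient can still be evaluable. On continuous dosing, 75% of 21 days is 0.75 x 21 = 15.75 days. Section 2 places the leukocyte nadir on cisplatin at days 18 to 23, after that mark and after the end of the days 1-10 schedule. Scheduled haematology is weekly (Table 4, footnote g), so after a first Grade 4 count the next scheduled count may already show recovery.

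**2. What could it do to an escalation decision?**

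Section 4.1 gives the rule: one DLT in 3 expands the cohort to at least 6, and 2 DLTs in up to 6 mark the dose as above the MTD. With DLT probability p and q = 1 - p, taking 6 as the expanded size:

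P(escalate) = q^3 + 3pq^2 x q^3

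The following are assumptions; none is in the protocol. The true DLT rate is 33%. A quarter to a half of it comes from the two duration criteria. Of those events, 50% to 100% are masked.

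| Duration share | Masked | Observed p | P(escalate) |
|---|---|---|---|
| any | 0% | 0.33 | 0.434 |
| 25% | 50% | 0.33 x (1 - 0.125) = 0.289 | 0.517 |
| 25% / 50% | 100% / 50% | 0.33 x (1 - 0.25) = 0.247 | 0.605 |
| 50% | 100% | 0.33 x (1 - 0.50) = 0.165 | 0.783 |

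Worked for the first row: 0.67^3 = 0.301; 3 x 0.33 x 0.67^2 = 0.444; 0.301 + 0.444 x 0.301 = 0.434.

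A second set of assumptions gives the same direction. Take independent risks of 10% for other DLTs and 20% for Grade 4 neutropenia beyond 5 days, so p = 1 - 0.90 x 0.80 = 0.28. The chance that the dose is declared not tolerated is then 0.464. If a quarter, a half or all of the prolonged cases are shortened, it falls to 0.368, 0.270 or 0.094.

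**The case against.** The strongest reply is that the loose reading of 4.5.7 is not the intended one. The paragraph opens on prophylaxis, so the relevant-event sentence may only mean secondary prophylaxis in later cycles. If any relevant event already permitted use in Cycle 1, the list of specific triggers that follows would be redundant. Read as the only Cycle 1 exceptions, those triggers fall at or after a DLT. Sections 4.5.3.1 and 4.5.3.2 are the dedicated haematological rules and cover the wait for the second cisplatin dose. Footnote b can be read together with footnote e.

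This stands in part. The loose reading is available, not compelled. But the relevant-event sentence applies to use during the study, with no cycle limit, and 4.5.7 points to 4.5.10 for its exceptions rather than to 4.5.3. Even on the strict reading, 4.5.7 permits triggers that 4.5.3.1 and 4.5.3.2 bar in Cycle 1.

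The second reply is that escalation is not a mechanical count. Section 4.1.1 bases it on all available data, section 7.6 requires a committee with at least 3 physicians, and section 4.1 provides further cohorts of three when toxicity is equivocal. Growth-factor use, with reasons, doses and dates, is recorded on the CRF (4.5.7). This also stands in part: a committee that notices early use can respond, but nothing requires the use to be flagged or says how the patient is counted.

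A reader might infer that every exception hides DLTs, or that counts from different sites cannot be pooled. The documents support neither. The difference between 4.5.3.1 and 4.5.3.2 by itself costs no DLT, and nothing shows that sites did follow different rules.

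**Conclusion.** The contradiction is explicit and does not depend on any assumption. Its consequence for the MTD is conditional: it arises only if growth factor is given early under the relevant-event sentence or footnote b, and only for Grade 4 neutropenia beyond 5 days or for delays driven by neutrophils. Delays caused by platelets or other toxicity are not at issue.

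A reader might infer that the MTD is biased upward. The protocol supports only that any such error would act in that direction. The size cannot be derived from it. The rise in the chance of escalation from 43% to 52-78% rests wholly on the assumed 33% rate, the assumed duration share and the assumed masking, and treats the cohort rule as automatic. With no masking the effect is zero, and committee review partly mitigates the rest. The point is worth correcting because one patient can change a decision in cohorts this small.

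**What to change.** 1. The sponsor should reconcile sections 4.5.3.1, 4.5.3.2, 4.5.7 and 4.5.10 and Table 6 footnotes b and e into one Cycle 1 statement that is consistent with the DLT definition in 4.1.2. Which clinical rule should apply is for the sponsor; this review does not say.
2. In 4.1.2, in the evaluability definition of 4.1.1 and in 7.4.5, state that a patient given growth factor in Cycle 1 before a duration-based DLT criterion could be assessed, and with no other DLT, is not counted as DLT-free and is flagged at the safety review.

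The cost is amendment wording and one flag from concomitant-medication data already collected on the CRF. The downside is that a cohort may occasionally need one more evaluable patient.

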#### 4.5.3.2 Management of Neutropenic Events

Cisplatin and AZD2281 may not be dosed until ANC  $\geq 1.5 \times 10^9/L$

Filgrastim or PEG-filgrastim may be instituted at the investigator's discretion at any time following completion of cycle 1. Cycle 1 is defined as the time period up until the second dose of cisplatin dose is administered). Filgrastim or PEG-filgrastim may be used at the investigator's discretion during cycle 1 only in the event of febrile neutropenia occurring during cycle 1.

Filgrastim doses can be rounded to within (plus or minus) 10% of the contents of one commercial vial or combinations of the commercial products; i.e., 300 or 480 micrograms/vial.

Each of the following neutropenic events will be managed in a sequential fashion as described in [Table 6](#).

1. ANC  $<1.0 \times 10^9/L$  on Day 1 of a cycle

2. Febrile neutropenia (ANC  $<1.0 \times 10^9/L$  with fever  $\geq 38.5^\circ C$ ) at any time
3. CTCAE grade 4 neutropenia (ANC  $<0.5 \times 10^9/L$ ) lasting longer than 5 days in the middle of a cycle

